3.4.2 Exploratory Efficacy Endpoints

Observed results, change from Baseline, and percent change from baseline for eGFR estimated by MDRD and creatinine will be summarized by visit using descriptive statistics.

Donor specific anti-HLA antibodies (DSA) (yes/no) will be summarized by visit using descriptive statistics.

Resolution of viremia will be generally defined as achieving a post-baseline viral load measure below the lower limit of quantification (<LLOQ) for that viral assay. The number of patients with resolution for each virus (BKV, CMV, EBV, AdV, JCV, and/or HHV-6) will be summarized by visit and at any visits. In addition, the proportion of patients reaching at least 1 log10 reduction or <LLOQ in BK viral load post infusion will be summarized by visit and at any visits.

LLOQ values for the viruses of interest are:

BKV Viral Load (Copy/mL): LLOQ = 156

Non-BK Target Viruses:

ADV Viral Load (Copy/mL): LLOQ = 32

CMV Viral Load (Copy/mL): LLOQ = 65.6

EBV Viral Load (Copy/mL): LLOQ = 37

HHV-6 Human Herpesvirus 6 (Copy/mL): LLOQ = 110

JCV JC Virus (IU/mL): LLOQ = 76

Time-to-event endpoints will be summarized using the Kaplan-Meier method. Number of patients with events and number of patients censored and reason of censoring will be presented along with estimate for the median time (days) and its 95% CI. Time-to-event will be presented using Kaplan-Meier plots.

Time to resolution of BK viremia will be calculated as starting at randomization for patients with detectable virus and ending at the first undetectable viral load (i.e., <LLOQ). Patients who discontinued from the study early or deceased before they are observed to have achieved resolution will be censored at the last assessment date for this endpoint.

For patients who reach the resolution of BK viremia, time to reappearance of BK viremia (duration of viral remission) will be calculated as starting at the first assessment with undetectable viral load and ending at the first detectable viral load (confirmed with 2 consecutive measures at least 8 days apart, or end of study if only one measure is available). Patients not demonstrating the reappearance of viremia would be censored on the date of the latest assessment for this endpoint. Patients who discontinued from the study early or deceased before they are observed to have will be censored at the last assessment date for this endpoint.

Time to resolution of non-BK target viral infections (i.e., associated signs, symptoms, and presence/absence of CMV, HHV-6, EBV, JCV, and/or AdV viremia) will not be performed due to limited number of events for each virus. The time to death will not be performed but the deaths will be summarized and listed.

To evaluate the impact of missing data at some timepoints, a sensitivity analysis will also be performed on BK viremia using last observation carried forward imputation.

In addition, the number and percentage for patients will be presented for following endpoints by visit unless otherwise stated.

- Patients with eGFR >20 mL/min/1.73m² at 24 weeks
- Patients with incidence of new target viral infections or recrudescent infections (i.e., BKV, CMV, EBV, AdV, JCV, and/or HHV-6) as defined by onset of viremia.
The associated symptoms are not collected so will not be considered.
- Patients with screening BK viremia <10,000 copies/mL who develop BK viremia \geq 10,000 copies/mL (sustained or non-sustained) or who experience reduction of immunosuppression which is defined as a reduction of 50% or greater of the current dose when compared to the dose at Baseline for the following medications: tacrolimus, Prograf, Envarsus, cyclosporine, Neoral Sandimmune, everolimus, sirolimus, Rapamune, rapamycin, mycophenolate mofetil, mycophenolate sodium, mycophenolic acid, Cell Cept, Myfortic, azathioprine).
 - The following drugs would not be considered for immunosuppression reduction: Prednisone, methylprednisolone, glucocorticoids, Leflunomide, Arava, Gammagard or IVIG.

Two sets of figures will be produced for mean+/- SD for change from baseline for eGFR for (Arm 1, Arm 2 and Arm 3) and (Arm 1+2 and Arm 3).

Two sets of figures will be produced for mean+/- SD for change from baseline for Creatinine for (Arm 1, Arm 2 and Arm 3) and (Arm 1+2 and Arm 3).

Listings will be provided for viral loads, eGFR, creatinine, HLA related information and donor specific anti-HLA antibodies.

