3 OBJECTIVES AND ENDPOINTS

Objectives	Endpoints
Primary 
 To compare the safety and tolerability of PSL to placebo in kidney transplant recipients 	
 Treatment-emergent adverse events (TEAEs) and changes in vital signs, physical exams, clinical laboratory assessments, and electrocardiograms (ECGs)
Key Secondary 
 To assess the overall efficacy of PSL to suppress plasma BK viral load compared with placebo 	
 Change in BK viremia in patients receiving PSL compared to patients receiving placebo
Other Secondary 
 To compare the relative efficacy of different dosing regimens of PSL to suppress BK viral load versus placebo 	
 Change in BK viremia in patients receiving different dosing regimens of PSL compared to patients receiving placebo
Exploratory 
 To assess change in estimated glomerular filtration rate (eGFR) over 24 weeks in recipients of PSL versus placebo 	
 Change in eGFR by Modified Dose in Renal Disease (MDRD) formula in recipients of PSL versus placebo

 To identify changes in donor-specific anti-human leukocyte antigen (anti-HLA) antibodies in recipients of PSL versus placebo 	
 Changes from baseline in levels of donor-specific anti-HLA antibodies in recipients of PSL versus placebo

 To determine the proportion of patients with resolution of BK viremia at 8 weeks post virus-specific T cell infusion 	
 Proportion of patients with resolution of BK viremia at 8 weeks post - Virus-Specific T cell infusion

 To assess kidney allograft survival at 24 weeks 	
 Proportion of patients with eGFR >20 mL/min at 24 weeks

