5.2 Exclusion Criteria

Medical Conditions

1. Undergone allogeneic hematopoietic cell transplantation.
2. Evidence or history of GVHD or CRS (Appendix 5 [[Section 10.5](#)] and Appendix 6 [[Section 10.6](#)], respectively).
3. Uncontrolled or progressive bacterial or fungal infections (ie, evidence of bacteremia, fungemia, dissemination, and/or organ-specific infection not well controlled by present therapies).
4. Uncontrolled or progressive viral infections (ie, evidence of viremia, dissemination, and/or organ-specific infection not well controlled by present therapies) not targeted by PSL.
5. Uncontrolled or progressive EBV-associated post-transplant lymphoproliferative disorder.
6. Known or presumed pneumonia.
7. Hemodynamic or respiratory instability defined as either of the following:
 - a. Requirement for continuous infusions of inotropes or vasopressors for blood pressure support.
 - b. Requirement for endotracheal intubation or mechanical ventilation.

8. Evidence of any medical condition that in the opinion of the Investigator might interfere with the patient's ability to participate in the trial.

Prior/Concomitant Therapy

9. Ongoing therapy with high-dose systemic corticosteroids (ie, prednisone dose >0.5 mg/kg/day or equivalent).
10. Patients who received, or are planned to receive, abatacept or belatacept, within 3 months of screening, or who received equine anti-thymocyte globulin ([ATG] Atgam®) or rabbit ATG (Thymoglobulin ®) in doses of >4.5 mg/kg or alemtuzumab (Campath-1H) or other immunosuppressive T cell-targeted monoclonal antibodies <28 days prior to randomization.

Prior/Concurrent Clinical Study Experience

11. Receipt of other investigational antiviral treatments (eg, anti-BK monoclonal antibodies) within 28 days or 5 half-lives (whichever is longer) prior to randomization.

Diagnostic assessments

12. Liver dysfunction, defined as liver transaminases (ie, aspartate aminotransferase or alanine aminotransferase) >5 times the upper limit of normal (ULN) or direct bilirubin >2 times the ULN reference per local laboratory.
13. Renal dysfunction, defined as estimated glomerular filtration rate (eGFR) (estimated by Modified Dose in Renal Disease [MDRD] formula) <20 mL/min/1.73 m².

Other Exclusions

14. Pregnant or nursing or planning to become pregnant.
15. ABO incompatible or complement-dependent lymphocytotoxic crossmatch positive transplant (isolated positive B cell crossmatches are not an exclusion criterion).
16. Weight <40 kg.

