2.1.3 Exploratory Objectives

The exploratory objectives include comparisons of the following in recipients of PSL and in patients receiving placebo:

- To assess change in estimated glomerular filtration rate (eGFR) over 24 weeks in recipients of PSL versus placebo
- To identify changes in donor-specific anti-human leukocyte antigen (anti-HLA) antibodies in recipients of PSL versus placebo
- To determine the proportion of patients with resolution of BK viremia at 8 weeks post virus-specific T cell infusion
- To assess kidney allograft survival at 24 weeks
- To assess the incidence of recrudescent or new infections with target viruses (including cytomegalovirus [CMV]), but principally BKV
- To determine whether patients with initially low BK viral load (ie, <10,000 copies/mL) can be prevented from developing viremia \geq 10,000 copies/mL that leads to new or increased immunosuppression reduction
- To determine whether patients with initially low BK viral load (ie, <10,000 copies/mL) in the investigational arm(s) develop lower viral loads than the placebo arm

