2.3.3 Exploratory Efficacy Endpoints

The exploratory efficacy endpoints include comparison between results in patients receiving PSL versus placebo for the following:

- Change in eGFR by Modified Dose in Renal Disease (MDRD) formula.
- Changes from baseline in levels of donor-specific anti-HLA antibodies.

- Proportion of patients with resolution of BK viremia at 8 weeks post virus-specific T cell infusion.
- Proportion of patients with eGFR >20 mL/min at 24 weeks.
- Incidence of new target viral infections or recrudescent infections (i.e., BKV, CMV, EBV, AdV, JCV, and/or HHV-6) as defined by onset of viremia and/or the presence of associated symptoms relative to baseline.
- Length of BKV remission (i.e., time from clearance of BK viremia to reappearance of BK viremia (plasma viral load >156 copies/mL \times 2 measures that are at least 2 weeks apart) or end of study).
- Number of patients with screening BK viremia < 10,000 copies/mL who develop BK viremia \geq 10,000 copies/mL (sustained or non-sustained) or who experience a medically significant event that leads to changes in immunosuppression reduction.
- The absolute viral load in patients in the investigational arms versus that in patients in the placebo arm with screening BK viremia <10,000 copies/mL.

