3.4.3 Other Endpoints

Observed results, change from baseline, and percent change from baseline for eGFR (estimated by the creatinine-cystatin C method) will be summarized by visit using descriptive statistics. The number of days of hospitalizations and re-hospitalizations for any reason will be summarized.

Number and percentage for patients will be presented for following endpoints.

- Patients with biopsy-proven acute allograft rejection. The results will be provided by severity (adjudicated Banff classification)
- Patients using immunosuppressive agents, including specific immunosuppressive agents used. The doses, and any changes in dose will be listed.
- Patients with kidney injury requiring hemodialysis
- Patients with hospitalizations/re-hospitalizations for any reason

The use of antiviral therapies will be listed as concomitant medications but not summarized.

The analyses for all the efficacy endpoints are summarized in Table 1:

Table 1: Efficacy Endpoints Summary and Statistical Analysis

| Type of Endpoint | Summary Table | |
|---|------------------------|---------------------|
| | Population | Variables[*]/Method |
| Continuous | | |
| • BK viral load | Observed/Chg/Pchg | |
| • eGFR by MDRD | Observed/Chg/Pchg | |
| • eGFR by Creatinine-cystatin C | Observed/Chg/Pchg | |
| Time to event [#] | | |
| • Time to BKV resolution | Kaplan-Meier | |
| • Duration of BKV remission | Kaplan-Meier | |
| Category | | |
| • BKV resolution | Categories: Yes/No | |
| • 1 Log10 reduction of BK viral post infusion | Categories: Yes/No | |
| • Patients with screening BK viremia <10,000 copies/mL develop BK viremia ≥10,000 copies/mL | Categories: Yes/No | |
| • Donor specific anti-HLA antibodies | Categories: Yes/No | |
| • eGFR >20 mL/min/1.73m ² | Categories: Yes/No | |
| • New viral infection | Categories: Yes/No | |
| • Immunosuppression reduction | Categories: Yes/No | |
| • Immunosuppressive agents | Categories: agent type | |
| • Biopsy-proven acute allograft rejection | Categories: severity | |
| • Kidney injury requiring hemodialysis | Categories: Yes/No | |
| Category and continuous | | |
| • Hospitalizations/re-hospitalizations | Yes/No; Duration | |

N/A = Not Applicable.

[*] Chg = Change from Baseline; Pchg = Percent Change from Baseline.

[\$] Line plot will be generated.

[#] Kaplan-Meier plot will be generated for each endpoint.

[**] Ratio is defined as unique clonotype donor DNA/patient DNA*100.

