3.5.2 Clinical Laboratory Tests

Laboratory assessments comprise safety laboratory tests (hematology, clinical chemistry and urinalysis) and other laboratory tests.

Descriptive statistics will be provided for clinical laboratory test results (hematology, clinical chemistry and routine urinalysis) and changes from baseline. With the exception of the LOCF sensitivity analysis of BK viremia, missing values for any of the laboratory evaluations will not be imputed; that is, only observed case data will be used.

A shift table, presenting the 2-way frequency tabulation for baseline and the worst post-baseline value according to the NCI CTCAE grade, will be provided for clinical laboratory.

In addition, the number and percentage of patients with the following potentially clinically significant abnormal liver function tests will be summarized:

- Potential Hy's Law cases: ALT or AST $\geq 3 \times \text{ULN}$ and total bilirubin $\geq 2 \times \text{ULN}$ and Alkaline phosphatase (ALP) $< 2 \times \text{ULN}$.

Listings will be presented for all laboratory data and all test values outside the normal range will be flagged.

In addition, other laboratory tests, including pregnancy test, serology test, testing for HIV, HCV, HBV and CMV, and donor specific anti-HLA antibodies will be presented in by-patient listings.

3.5.3 *Vital Signs*

Descriptive statistics will be provided for vital signs (including blood pressures, pulse rate, respiratory rate, oximetry, and body temperature), body weights, and BMIs by treatment group at each scheduled visit. Changes from baseline will also be summarized.

All vital sign data will be listed by patient.

3.5.4 *Electrocardiograms*

ECG measurements include heart rate (bpm), measures PR (msec), QRS (msec), QT (msec), and QTc (msec) (corrected using Fridericia's and Bazett's methods). Descriptive statistics will be provided for the observed measurements and change from baseline.

All ECG parameters and the Investigator interpretation of findings including details of any abnormalities will be listed by patient.

3.5.5 *Physical Examinations*

All abnormal physical examination findings, including details of any abnormalities will be listed by patient.

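### The donor-specific antibody endpoint is change from baseline in level, but the SAP's only summary is yes/no by visit, which leaves within-patient change unsummarised by arm

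*SAP*

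**What the plan says.** The endpoint is worded the same way in both documents. Protocol section 3 gives "Changes from baseline in levels of donor-specific anti-HLA antibodies in recipients of PSL versus placebo", and SAP 2.3.3 gives "Changes from baseline in levels of donor-specific anti-HLA antibodies". The objective behind it, in SAP 2.1.3, is "To identify changes in donor-specific anti-human leukocyte antigen (anti-HLA) antibodies in recipients of PSL versus placebo".

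The planned analysis is in SAP 3.4.2: "Donor specific anti-HLA antibodies (DSA) (yes/no) will be summarized by visit using descriptive statistics". SAP Table 1 (section 3.4.3) agrees with that text. It places the variable among the categorical endpoints, "Donor specific anti-HLA antibodies | Categories: Yes/No", whereas BK viral load and both eGFR measures are continuous endpoints with observed value, change and percent change.

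Two listings are planned. SAP 3.4.2 states: "Listings will be provided for viral loads, eGFR, creatinine, HLA related information and donor specific anti-HLA antibodies". SAP 3.5.2 states: "donor specific anti-HLA antibodies will be presented in by-patient listings". Neither says whether a level or only a positive/negative result is listed.

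DSA is sampled at Day 1, Week 12 and Week 24 or early termination (Protocol section 1.3, Tables 1 and 2).

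**The concern.** The endpoint has two parts that the planned table lacks: a level, and a change within the patient. A count of positives at each visit describes prevalence. It mixes antibodies present at entry with antibodies that appeared during the study, and it cannot register a rise in a patient who was already positive.

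This has some weight here because Protocol 2.4.1 and 4.2 name development of DSA as a harm linked to immunosuppression reduction, and 2.4.1 argues that PSL may do better than that standard of care. New DSA and rising DSA are the observations that bear on that argument. A table of equal counts at two visits could be read as no change when some patients have gained antibodies and others have lost them.

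The SAP gives reasons for other departures from the protocol. In section 3.4.2 it says that associated symptoms were not collected and that the time-to-resolution analysis for non-BK viruses is dropped for lack of events. It gives no reason for replacing level with yes/no.

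**Working it through.** There is no planned figure to reproduce. The endpoint has no effect size, alpha or power attached, and Protocol 9.1 rules out formal hypothesis tests. The check is what the planned table can identify.

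**Inputs**
- Patients per arm: n = 20, so 40 for pooled PSL (Protocol 9.2).
- Baseline-positive patients are eligible: none of the exclusion criteria in Protocol 5.2 concerns DSA. The Amendment 1 rationale says why the exclusion was removed: central-laboratory results at randomization and later can be compared.
- Paired samples: Day 1 with Week 12, and Day 1 with Week 24 or early termination (Protocol 1.3).
- DSA prevalence and conversion rates: not given. All counts below are assumed, with complete data at both visits.

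**What the by-visit counts determine**

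Let a be the number positive at baseline, b the number positive later, d the number turning positive (de novo) and l the number turning negative. Then b = a − l + d, so d = b − a + l. Since l lies between 0 and a, and d between 0 and n − a:

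max(0, b − a) ≤ d ≤ min(b, n − a)

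| n | a | b | Lower limit | Upper limit | De novo count |
|---|---|---|---|---|---|
| 20 | 6 | 6 | max(0, 0) | min(6, 14) | 0 to 6 |
| 20 | 4 | 4 | max(0, 0) | min(4, 16) | 0 to 4 |
| 20 | 4 | 6 | max(0, 2) | min(6, 16) | 2 to 6 |
| 20 | 6 | 4 | max(0, −2) | min(4, 14) | 0 to 4 |
| 20 | 0 | 4 | max(0, 4) | min(4, 20) | exactly 4 |
| 40 | 8 | 8 | max(0, 0) | min(8, 32) | 0 to 8 |
| 40 | 8 | 12 | max(0, 4) | min(12, 32) | 4 to 12 |

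For 6/20 then 6/20, the de novo proportion among the 14 baseline-negative patients could be anything from 0/14 = 0% to 6/14 = 43%.

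**What a shift table determines**

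Suppose that 2 of the 6 baseline positives lose DSA and 2 of the 14 baseline negatives gain it. The planned table still reads 6/20 and 6/20. The shift table reads 4 positive/positive, 2 positive/negative, 2 negative/positive and 12 negative/negative. The de novo proportion is 2/14 = 14%, with an exact 95% CI of 1.8% to 42.8%.

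**Levels**

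A patient positive at both visits is counted as yes at both, whatever the level does. If 4 baseline positives all tripled in level, the table would show 4 and 4.

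**The case against.** The strongest reply has four parts.

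1. *The data are not lost.* Two by-patient listings are planned, and with about 60 patients and three scheduled samples each, a reader could trace conversions by hand. This stands against any inference that new DSA or rising levels would never appear in the output: conversions could be traced, and so could levels if they are listed. It does not supply the PSL-versus-placebo summary of change that the endpoint names.

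2. *The counts carry some information on new DSA.* A net rise in positives gives a lower bound, and with no positives at baseline the count is exact. A reader might infer that the table cannot show de novo DSA at all; that is too strong. What stands is that the number is not identified when some patients are positive at baseline, and the entry criteria do not allow a baseline of zero to be assumed. The crossmatch criterion, "ABO incompatible or complement-dependent lymphocytotoxic crossmatch positive transplant", is a related restriction on entry. It neither bars existing DSA nor proves that such patients are admitted; the point rests on the absence of any DSA exclusion.

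3. *Safety monitoring does not rest on DSA.* A reader might take DSA as the trial's main signal of alloimmune harm from third-party cells. The documents do not say so. The events of special interest are infusion-related events, GVHD and CRS (Protocol 8.3.7), adjudicated biopsy-proven rejection is tabulated (SAP 3.4.3), and the risk section (Protocol 2.4.2) does not mention DSA. The documents link DSA to immunosuppression reduction.

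4. *A numeric level may not exist.* Protocol 8.1.3 says only that a flow cytometric method is used, with no unit or cut-off. This also stands, so a summary of level has to be conditional. It then becomes a reason to correct the endpoint wording, not to leave the mismatch.

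**Conclusion.** Wrong as written: the planned analysis does not match the defined endpoint. Following the SAP exactly produces DSA prevalence by visit, with no summary by arm of change in level or change in status. The mismatch itself rests on the text alone and needs no assumption.

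The size of the consequence depends on baseline prevalence, which the documents do not give. If no patient is positive at entry, the by-visit counts give de novo DSA exactly. If some are, the count is known only within max(0, b − a) to min(b, n − a), for example 0 to 6 for an assumed 6/20 then 6/20. The 14% in the worked example is a constructed case in which gains and losses cancel. It shows that the problem can occur, and it is not an estimate. Missing follow-up samples would add further uncertainty.

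The endpoint is exploratory and descriptive. No sample size, alpha, primary or key secondary conclusion changes.

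**What to change.** In SAP 3.4.2 and Table 1:

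- Keep the yes/no counts by visit, which remain useful as prevalence.
- Add shift tables from baseline to Week 12 and from baseline to Week 24, by arm, among patients with both results. Give the number and percentage with de novo DSA among baseline-negative patients. An exact 95% CI is optional, since Protocol 9.4.4 asks only for counts and percentages for exploratory categorical endpoints.
- State how the laboratory defines a positive result.
- If the laboratory reports a numeric level, summarise observed level and change from baseline by arm at Weeks 12 and 24, and include the level in the listing.
- If it reports only positive/negative, say so, reword the endpoint in SAP 2.3.3 as change in DSA status, and record this as a departure from Protocol section 3.

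The cost is one added table specification for the shifts, plus either a standard continuous summary or a change of wording. The paired samples are already scheduled, so no visit or blood draw is added.

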8.1.1 Viral Load

In patients with concomitant viral infections at the time of treatment, peripheral blood and, where relevant, urine, will be monitored for BKV, CMV, AdV, EBV, JCV, and/or HHV-6 viral load (see [Section 1.3](#)). Resolution of viral infection will be defined as a return to undetectable as defined by the assay used and complete resolution of clinical signs and symptoms as determined by the Investigator. Viral load will be quantitated using polymerase chain reaction assays.

Samples for viral sequence/genotype will be collected on all patients as indicated in [Section 1.3](#).

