3.2 Analysis Populations

3.2.1 Intent-to-Treat (ITT) Population

The Intent-to-Treat (ITT) Population will include all randomized patients regardless of whether the patient actually receives PSL or placebo. Patients will be analyzed according to the randomized study treatment.

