3.4 Efficacy Analyses

This section describes the analysis to be conducted for the key secondary, other secondary and exploratory efficacy endpoint along with other endpoints. The efficacy analysis will be performed on the ITT population unless otherwise stated. Analyses using mITT may be set aside if it is determined that the ITT population and the mITT Population are identical. Unless otherwise specified, the results of efficacy analysis and all the summary tables will be presented by stratum and treatment group.

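### The per-virus resolution count in SAP 3.4.2 has no baseline-viremia condition, so read literally it counts patients who never had the non-BK virus as resolved

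*SAP*

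**What the plan says.** SAP 3.4.2 gives the rule: "Resolution of viremia will be generally defined as achieving a post-baseline viral load measure below the lower limit of quantification". The next sentence sets its scope: "The number of patients with resolution for each virus (BKV, CMV, EBV, AdV, JCV, and/or HHV-6) will be summarized by visit and at any visits". Neither sentence mentions the baseline value or a denominator.

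The population comes from SAP 3.4, "The efficacy analysis will be performed on the ITT population unless otherwise stated", and SAP 3.2.1, "The Intent-to-Treat (ITT) Population will include all randomized patients regardless of whether the patient actually receives PSL or placebo".

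Other parts of the documents do carry a baseline condition:

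- Later in SAP 3.4.2: "Time to resolution of BK viremia will be calculated as starting at randomization for patients with detectable virus".
- Protocol 8.1.1, which concerns patients with concomitant viral infections at the time of treatment: "Resolution of viral infection will be defined as a return to undetectable". It also asks for clinical signs and symptoms to resolve.
- SAP 2.3.4 limits time to resolution of non-BK infections to those present at randomization. SAP 3.4.2 then says this analysis "will not be performed due to limited number of events for each virus".

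The companion row in SAP 3.4.2, "Patients with incidence of new target viral infections or recrudescent infections", is defined by onset of viremia and covers all six viruses. The endpoint as listed in SAP 2.3.3 adds that onset is judged relative to baseline. The restatement in 3.4.2 leaves that phrase out.

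**The concern.** The trial selects patients for BK viremia. No inclusion criterion in Protocol 5.1 asks for any other target virus, and the schedule of activities first measures the other five on Day 1. Many patients may therefore be below the limit for a given non-BK virus from the start. A rule that asks only for a post-baseline value below the limit cannot tell a patient who cleared a virus from one who never had it.

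The at-any-visit summary is the most exposed, because one value below the limit is enough. SAP 3.1.5 sets values below the limit of quantification to just under it, so an uninfected patient passes the test in code without any special handling.

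With non-BK time to resolution dropped, this count is the only non-BK resolution summary left. The product is described as specific for these viruses (Protocol 6.1), so a high count in every arm could be misread as activity against them, and a real difference among infected patients would be diluted.

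**Working it through.** **Reproduction.** The plan states no resolution rate, event count or power for this endpoint, so there is no figure to reproduce. The check is a reading of the text followed by an illustration.

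**Step 1: does any text supply the condition for the count?**

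| Place | Applies to | Baseline condition |
|---|---|---|
| SAP 3.4.2, resolution count | all six viruses | none |
| SAP 3.4.2, time to resolution | BKV only | detectable virus |
| SAP 2.3.4, time to resolution | non-BK viruses | present at randomization; analysis dropped |
| Protocol 8.1.1 | concomitant infections | return to undetectable |

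The condition appears in the neighbouring rules but not in the count itself.

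**Step 2: is BKV affected?** Inclusion criterion 3b requires 350 to 10,000,000 copies/mL at screening, and the BKV LLOQ in SAP 3.4.2 is 156. Since 350 > 156, every eligible patient is above the limit at screening. A Day 1 baseline value could still fall below 156, but BKV is essentially unaffected.

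**Step 3: illustration for one non-BK virus.** The arm size n = 20 is from SAP 2.2.3. Baseline prevalence p and true clearance r among viremic patients are assumptions, because the documents give neither. Patients below the limit at baseline are assumed to have at least one later value below it.

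- Literal count = n(1 − p) + n·p·r
- Restricted count = n·p·r out of n·p

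| p | Viremic at baseline | Literal, r = 20% | r = 50% | r = 80% |
|---|---|---|---|---|
| 5% | 1 | 19.2/20 = 96% | 19.5/20 = 97.5% | 19.8/20 = 99% |
| 10% | 2 | 18.4/20 = 92% | 19.0/20 = 95% | 19.6/20 = 98% |
| 20% | 4 | 16.8/20 = 84% | 18.0/20 = 90% | 19.2/20 = 96% |
| 30% | 6 | 15.2/20 = 76% | 17.0/20 = 85% | 18.8/20 = 94% |

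The share of counted patients who were below the limit at baseline runs from 14/18.8 = 74% to 19/19.2 = 99%. At p = 10% and r = 50%, the literal rule gives 19/20 (95%) and the restricted rule 1/2 (50%).

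**Step 4: dilution between arms.** With the same p in both arms, the literal difference is p × (r₁ − r₂). For an assumed 80% versus 20% clearance, a 60-point difference among viremic patients becomes 0.05 × 60 = 3, 0.10 × 60 = 6, 0.20 × 60 = 12 and 0.30 × 60 = 18 points.

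**Step 5: whole-trial example.** If 6 of 60 patients are CMV viremic on Day 1 and none clears, the literal rule reports at least 54/60 = 90% resolved, against 0/6. With 3 viremic it reports at least 57/60 = 95%, against 0/3.

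**The case against.** **Intent.** The strongest reply is that the authors meant infected patients. A patient without viremia has none to resolve, the definition is hedged as holding generally, and Protocol 8.1.1 speaks of a return. The stated reason for dropping non-BK time to resolution, too few events, makes sense only if uninfected patients are not events. This stands as evidence of intent. It does not supply a programmable rule, and the same section states the condition where it wants it.

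**Stakes.** Non-BK resolution is not a listed exploratory endpoint in SAP 2.3.3, SAP Table 1 lists only BKV resolution, no formal testing is planned (Protocol 9.1), and viral loads are listed by patient. All of this stands and keeps the point minor. The count sentence promises a number of patients and not a percentage, but SAP 3.1.4 gives percentages by default for categorical variables.

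**Stronger readings.** A reader might infer that the non-BK counts will be close to 100% in every arm. The documents do not show that: they give no prevalence, and the remark about few events is consistent with low prevalence without proving it.

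A reader might also infer that the new/recrudescent row has no at-risk set and would penalise the arm that clears more BK viremia. With assumed clearance of 40% versus 10% and relapse of 30% versus 50%, the row would show 0.40 × 0.30 = 12% on PSL against 0.10 × 0.50 = 5% on placebo, while 0.40 × 0.70 = 28% versus 0.10 × 0.50 = 5% cleared and stayed clear. The documents do not support treating this as a flaw in the endpoint. SAP 2.3.3 already says relative to baseline, and recrudescence by definition follows clearance. SAP 3.4.2 also reports BKV resolution by visit and analyses reappearance by Kaplan-Meier among patients who cleared. Dropping BKV from the row would contradict the objective in SAP 2.1.3, which names BKV as its principal virus. What remains is a presentation point: 3.4.2 should carry over the baseline phrase and show BKV separately.

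**Conclusion.** The point holds as a missing condition in a stated rule. Taken literally, SAP 3.4.2 counts patients who never had CMV, EBV, AdV, JCV or HHV-6 viremia as resolved, contrary to Protocol 8.1.1 and out of step with the SAP's own BK time-to-resolution rule. The percentages in the illustration rest on assumed prevalence and clearance and on each baseline-negative patient having a later value below the limit. They show how the error behaves, and its actual size cannot be known from the documents. No primary or secondary result is touched. Severity: minor.

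**What to change.** In SAP 3.4.2, add after the definition: resolution of each virus is assessed only in patients whose baseline value is at or above the LLOQ for that virus, and the number of such patients is reported as the denominator by arm. State that viremia first appearing after baseline belongs in the new-infection row, and that patients without a baseline value for a virus are shown separately. Say how the virological definition relates to Protocol 8.1.1, which also requires signs and symptoms to resolve.

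In the new/recrudescent row, restore the relative-to-baseline wording from SAP 2.3.3. Count new non-BK infection among patients below the LLOQ at baseline. Keep BKV, but as a separate recrudescence row among patients who cleared, placed next to the clearance counts.

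The cost is SAP wording and changed denominators, with no new data. The drawback is small non-BK denominators: 1 to 6 patients per arm at the assumed 5% to 30% prevalence (20 × 0.05 = 1; 20 × 0.30 = 6).
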